## Methods

The study will be conducted with IRB approval and written informed consent. The trial will be registered at ClinicalTrials.gov before the first patient is enrolled.

### **Subject selection**

We will enroll patients having laparoscopic major abdominal or pelvic surgery, or similarly large operations. Patients who chronically use opioids will *not* be excluded. Both men and women will be recruited, and we will encourage under-represented minorities to participate. **We will enroll up to a maximum of 144 adult patients.**

#### **Inclusion criteria**

- 1) Adults having major non-cardiac surgery expected to last  $\geq 2$  hours;
- 2) American Society of Anesthesiologists physical status 1-3;
- 3) Age 21-85 years old;
- 4) Planned endotracheal intubation.

#### **Exclusion criteria**

- 1) Planned neuraxial or regional block;
- 2) Clinician preference for an opioid other than, or in addition to, fentanyl;
- 3) Non-sinus heart rhythm;
- 4) Neurologic condition that, in the opinion of the investigators, may preclude accurate assessment of postoperative pain and nausea;
- 5) Lack of English language fluency;
- 6) Routine user of psychoactive drugs other than opioids;
- 7) Contraindication to sevoflurane, fentanyl, morphine, or ondansetron.

- 8) Intracranial surgery.
- 9) BMI > 40

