## **Protocol**

Patients will be premedicated with 0-2 mg midazolam per preference of the attending anesthesiologist. General anesthesia will be induced as preferred by the attending anesthesiologist, usually with a combination of lidocaine 1 mg/kg, propofol 1-4 mg/kg, fentanyl 1-2 µg/kg, and rocuronium 0.6-1.2 mg/kg or succinylcholine 1.5 mg/kg, as clinically appropriate. The trachea will be intubated and the lungs will be mechanically ventilated per clinical routine. General anesthesia will be maintained with sevoflurane at a target concentration of 0.7 %, with the dose being adjusted based on apparent clinical need, supplemented with fentanyl. Sevoflurane will be given per clinical routine and adjusted as usual in response to vital signs, surgical need, etc. Nitrous oxide will not be used for induction or during anesthetic maintenance. Vasopressors, antihypertensives, and drugs to control heart rate may be given as clinically indicated. Depth of anesthesia will be recorded for all patients using BIS.

Unless another opioid is clinically indicated, fentanyl will be the only opioid used for induction and throughout anesthesia. Long-acting opioids such as morphine will not be given. No opioid will be given unless clinically indicated from the end of surgery until patients reach the recovery unit.

Patients will be randomized 1:1, stratified for pre-operative chronic opioid use, with random-sized blocking to NOL guided analgesic management or routine care. The randomization table will be prepared by trial statisticians, and allocation will be concealed until shortly before anesthetic induction with a web-based randomization system.

- 1) **Routine opioid management.** Clinicians will be blinded to NOL monitoring and use clinical judgement to determine how much fentanyl should be given, and when. Clinical judgement will be according to their standard practice and may include interpretation of blood pressure, heart rate, diaphoresis, tearing, and pupil size. Boluses of fentanyl 1 µg/kg actual body weight (ABW), up to a maximum dose of 100 µg per bolus, can be given per clinical judgement.  
**Towards the end of the surgery (approximately 30-45 minutes before end of surgery, based on clinical judgment), the boluses of fentanyl will be reduced to 0.5 µg/kg ABW, up to a maximum of 50 µg per boluses. Boluses will be given per clinical judgment.**

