- 2) **NOL-guided opioid administration.** Clinicians will titrate fentanyl to keep NOL under 25 — *always using good clinical judgement for individual patients.*

NOL values exceeding 25 for more than 30 seconds will typically be treated with boluses of fentanyl 1 $\mu$ g/kg ABW, up to a maximum of 100  $\mu$ g per boluses, 5-minute intervals. Towards the end of the surgery (approximately 30-45 minutes before end of surgery, based on clinical judgment), the boluses of fentanyl will be reduced to 0.5  $\mu$ g/kg ABW, up to a maximum of 50  $\mu$ g per boluses, 5 minutes intervals. The target of a NOL score below 25 will be maintained until surgery ends.

Approximately 20-30 minutes before end of the surgery, a preemptive bolus of hydromorphone will be given intravenously per clinical routine;

- Patients younger than 70 years: 0.4 mg of hydromorphone for patients with an ABW <60 kg and 0.6 mg of hydromorphone for patients with an ABW > 60 kg
- Patients aged between 70 and 75 years: 0.4 mg of hydromorphone,
- Patients older than 75 years: 0.2 mg of hydromorphone.

Near the end of surgery, 4 mg ondansetron will be given intravenously per clinical routine. Upon completion of surgery, sevoflurane will be discontinued. Neuromuscular block will be reversed with sugammadex per clinician preference. At the end of the surgical procedure, patients will be extubated and transferred to the post anesthesia care unit (PACU).

Surgical pain will be treated with boluses of intravenous morphine/ hydromorphone per clinical routine by nurses blinded to intraoperative randomization. PCA will be activated upon arrival to PACU, per routine care. Generally, rescue boluses are given when verbal response pain scores are  $\geq 4/10$ , but consistent postoperative analgesic management will be at the discretion of the postoperative clinical team. Nausea and vomiting will be initially treated by intravenous injection of 4mg ondansetron per clinical routine. Alternative anti-emetics will be administered as clinically indicated.

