- Protocol: we now specify for the NOL-guided opioid administration group, that NOL values above 25 **exceed 60 or more seconds**, before a fentanyl bolus should be given.
- Protocol: we now specify, that all patients will receive a morphine **PCA**, which will be activated upon arrival to **PACU**, per routine care.
- Measurements: we now define inadequate analgesia: **inadequate analgesia will be defined by systolic pressure  $\geq 140$  mmHg, heart rate exceeding 90 beats/min, MAP<65 mmHg. Vasoactive drugs and episodes and duration of hypotension (mean arterial pressure <65 mmHg, occurrences of MAP <60 & MAP <55) will be recorded. Muscle-relaxant administration will be recorded as well.**
- Measurements: we now define documented medications and measurements in more details: **The following will be recorded on the PMD-200 monitor, using the EVENTS button, as accurately as possible: Medications administration: Fentanyl, Vasoactive drugs, Muscle relaxants, Reversal agents; Events: Induction, Intubation, Foley catheter placement, Incision, Insufflation, Trocar insertion, Discontinuation of sevoflurane, Extubation.**
- We added two paragraphs about **Adverse Events** and **Reporting procedures**.

- Title: “benefits” was replaced by “consequences”
- Several Co-investigators have been added.
- Aims and hypothesis have been revised.
- Methods: subject selection. “We will enroll up to 144 adult patients.” (replaced 30 cases)
- Inclusion criteria: “Morphine PCA as clinical standard postoperatively” was removed and is now considered optional
- Number of pilot patients: we will now enroll up to **25 pilot patients** (replacing 10 patients)
- Study protocol: Routine opioid management. We now specify the bolus of fentanyl: **“Boluses of fentanyl 1 µg/kg actual body weight (ABW), up to a maximum dose of 100 µg per bolus”** ...Towards the end of the surgery (approximately 30-45 minutes before end of surgery, based on clinical judgment), the boluses of fentanyl will be reduced to 0.5 µg/kg ABW, up to a maximum of 50 µg per boluses. Boluses will be given per clinical judgment.

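### The contraindication screen in exclusion 7 omits hydromorphone, which the protocol schedules before the end of surgery and names again for PACU analgesia

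*Combined protocol and SAP*

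**What the plan says.** Exclusion criteria, item 7, screens for four drugs: "Contraindication to sevoflurane, fentanyl, morphine, or ondansetron".

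The Protocol section, in the text after the NOL-guided item, states that "a preemptive bolus of hydromorphone will be given intravenously per clinical routine" about 20-30 minutes before the end of surgery. Doses are tiered by age (under 70, 70 to 75, over 75) and, in the youngest tier, by weight. The same section says of the recovery unit: "Surgical pain will be treated with boluses of intravenous morphine/ hydromorphone per clinical routine by nurses blinded to intraoperative randomization".

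Earlier in the Protocol section, fentanyl is to be the only opioid through anaesthesia unless another is clinically indicated, and "Long-acting opioids such as morphine will not be given".

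The only other exclusion that refers to the choice of opioid is item 2: "Clinician preference for an opioid other than, or in addition to, fentanyl".

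**The concern.** A contraindication criterion exists so that nobody is randomised into a trial that then plans to give them a drug they should not have. Exclusion 7 does this for the volatile anaesthetic, the titrated opioid, one of the two recovery-unit opioids and the antiemetic. It does not do it for hydromorphone, which has a stated time window and stated dose tiers.

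For an affected patient, eligibility and treatment plan disagree, and the disagreement comes to light in the operating room after allocation. If the bolus is then withheld, the patient remains in the modified intent-to-treat set, because that set keeps everyone randomised who received any of the study intervention. The standardised end-of-surgery opioid would be missing shortly before the 60 minutes in which the primary pain scores are taken. Screening before randomisation avoids both the safety question and the deviation.

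**Working it through.** The plan gives no figure to reproduce. The main check compares the eligibility list with the drugs named in the Protocol section.

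| Drug | In exclusion 7? | Role in the Protocol section |
|---|---|---|
| Sevoflurane | Yes | Maintenance, following clinical routine |
| Fentanyl | Yes | Induction and intraoperative titration |
| Ondansetron | Yes | Near the end of surgery and for recovery-unit nausea, following clinical routine |
| Morphine | Yes | Not given during anaesthesia; one of two recovery-unit options |
| Hydromorphone | No | Bolus about 20-30 minutes before end of surgery; the other recovery-unit option |
| Midazolam, lidocaine, propofol, rocuronium, succinylcholine, sugammadex | No | Left to clinician preference |

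**Step 1: does another criterion cover hydromorphone?** The four inclusion criteria concern surgery type and duration, ASA status, age and intubation. The other exclusions concern regional block, clinician opioid preference, heart rhythm, neurologic condition, language, psychoactive drug use, intracranial surgery and BMI. None addresses a contraindication to hydromorphone. Item 2 is about what the clinician prefers, not what the patient can receive.

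**Step 2: whom does the bolus reach?** The eligible age range is 21-85 years, and the three age tiers span it. The text does not make clear whether the bolus applies to both arms or only to the NOL-guided arm. The gap exists wherever the bolus applies.

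**Step 3: does the routine-care qualifier explain the omission?** No. Ondansetron carries the same qualifier ("Near the end of surgery, 4 mg ondansetron will be given intravenously per clinical routine") and is screened. So does sevoflurane.

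**Step 4: who is affected?** Only patients contraindicated to hydromorphone and to neither fentanyl nor morphine, because a contraindication to either of those already excludes. Anyone contraindicated to opioids generally is already screened out. The documents give no prevalence for the remaining group.

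**Step 5: could this move the primary result?** With 1:1 allocation and a maximum of 144 patients, an arm has 144/2 = 72. If k affected patients all fell in one arm and each scored d points worse, the arm mean would shift by k × d / 72. The values below are assumptions chosen to show scale, not estimates.

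- k = 1, d = 3: 3/72 = 0.042 points
- k = 3, d = 3: 9/72 = 0.125 points

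The planned difference is 1.25 points, so these shifts are about 3% (0.042/1.25) and 10% (0.125/1.25) of it. Both put every affected patient in the same arm. A contraindication on record before randomisation is balanced between arms in expectation, so no systematic shift is expected from how these patients are allocated.

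**The case against.** The strongest reply is that nothing in the protocol obliges anyone to give a contraindicated drug. The bolus follows clinical routine, and the Human Subjects Protection section says that clinical judgement prevails in all cases. The realistic outcome is a withheld bolus, not an exposure. This stands, and it is the main reason the point is minor. It does not close the gap, because that safeguard acts after randomisation and an eligibility criterion acts before.

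A second reply is that exclusion 7 was never a full drug list, since the induction agents, relaxants and reversal agent are also absent. That is true, but those drugs are left to the clinician's choice. Hydromorphone is named with a window and dose tiers.

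A third is that the bolus itself conflicts with the statements that fentanyl is the only opioid and that "Long-acting opioids such as morphine will not be given". If those prevailed, hydromorphone would not be scheduled during surgery. This also stands, and it is why the passages should be reconciled together. Even then, hydromorphone would remain a recovery-unit drug on equal terms with morphine, which is screened.

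A reader might infer three stronger claims that the documents do not support:

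- **Exclusion 7 is the only protection against a contraindicated drug.** It is the only eligibility item on the subject, but clinical judgement remains as a safeguard.
- **Screening for morphine is itself a fault.** It is not: recovery-unit staff may give morphine, so excluding patients who cannot receive it is reasonable.
- **The omission biases the primary comparison because the anaesthesia clinicians are unblinded.** A documented contraindication predates allocation, and withholding the drug would follow the record, not the arm.

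**Conclusion.** The mismatch is real and can be read directly from the current text: hydromorphone is scheduled, and named for recovery, without being in the contraindication screen. A patient contraindicated to it, but not to fentanyl or morphine, meets the written criteria.

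The point is minor. The number affected is unknown, probably very small and possibly zero, and the documents support no estimate. The effect on the primary result is negligible. The case rests on patient safety and on agreement between two stated rules, not on bias or power. It assumes that hydromorphone stays in the protocol as a bolus, as a recovery-unit drug, or both.

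The List of changes fits a simple explanation. It records the standardisation of the hydromorphone bolus, while the only change it records to the exclusion criteria is the BMI limit. That suggests exclusion 7 was not revisited, but the log does not say so.

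**What to change.** At the next amendment, reconcile exclusion 7 with the two parts of the Protocol section that bear on it: the fentanyl-only and no-long-acting-opioid statements, and the hydromorphone bolus with the recovery-unit analgesia text. The reconciliation should also settle how exclusion 2 is to be read alongside a scheduled second opioid. Then word exclusion 7 so that the contraindication screen covers every opioid the reconciled protocol names, including hydromorphone if it remains in either role. Update the screening checklist to match. Which opioids are given, when and at what dose is for the sponsor and investigators to settle; nothing is proposed on that here.

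For exclusion 7 itself the cost is a word or a line in the criteria and one checklist item. The downside is possibly a very few fewer eligible patients.

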## **Protocol**

Patients will be premedicated with 0-2 mg midazolam per preference of the attending anesthesiologist. General anesthesia will be induced as preferred by the attending anesthesiologist, usually with a combination of lidocaine 1 mg/kg, propofol 1-4 mg/kg, fentanyl 1-2 µg/kg, and rocuronium 0.6-1.2 mg/kg or succinylcholine 1.5 mg/kg, as clinically appropriate. The trachea will be intubated and the lungs will be mechanically ventilated per clinical routine. General anesthesia will be maintained with sevoflurane at a target concentration of 0.7 %, with the dose being adjusted based on apparent clinical need, supplemented with fentanyl. Sevoflurane will be given per clinical routine and adjusted as usual in response to vital signs, surgical need, etc. Nitrous oxide will not be used for induction or during anesthetic maintenance. Vasopressors, antihypertensives, and drugs to control heart rate may be given as clinically indicated. Depth of anesthesia will be recorded for all patients using BIS.

Unless another opioid is clinically indicated, fentanyl will be the only opioid used for induction and throughout anesthesia. Long-acting opioids such as morphine will not be given. No opioid will be given unless clinically indicated from the end of surgery until patients reach the recovery unit.

Patients will be randomized 1:1, stratified for pre-operative chronic opioid use, with random-sized blocking to NOL guided analgesic management or routine care. The randomization table will be prepared by trial statisticians, and allocation will be concealed until shortly before anesthetic induction with a web-based randomization system.

- 1) **Routine opioid management.** Clinicians will be blinded to NOL monitoring and use clinical judgement to determine how much fentanyl should be given, and when. Clinical judgement will be according to their standard practice and may include interpretation of blood pressure, heart rate, diaphoresis, tearing, and pupil size. Boluses of fentanyl 1 µg/kg actual body weight (ABW), up to a maximum dose of 100 µg per bolus, can be given per clinical judgement.  
**Towards the end of the surgery (approximately 30-45 minutes before end of surgery, based on clinical judgment), the boluses of fentanyl will be reduced to 0.5 µg/kg ABW, up to a maximum of 50 µg per boluses. Boluses will be given per clinical judgment.**
- 2) **NOL-guided opioid administration.** Clinicians will titrate fentanyl to keep NOL under 25 — *always using good clinical judgement for individual patients.*

NOL values exceeding 25 for more than 30 seconds will typically be treated with boluses of fentanyl 1 $\mu$ g/kg ABW, up to a maximum of 100  $\mu$ g per boluses, 5-minute intervals. Towards the end of the surgery (approximately 30-45 minutes before end of surgery, based on clinical judgment), the boluses of fentanyl will be reduced to 0.5  $\mu$ g/kg ABW, up to a maximum of 50  $\mu$ g per boluses, 5 minutes intervals. The target of a NOL score below 25 will be maintained until surgery ends.

Approximately 20-30 minutes before end of the surgery, a preemptive bolus of hydromorphone will be given intravenously per clinical routine;

- Patients younger than 70 years: 0.4 mg of hydromorphone for patients with an ABW <60 kg and 0.6 mg of hydromorphone for patients with an ABW > 60 kg
- Patients aged between 70 and 75 years: 0.4 mg of hydromorphone,
- Patients older than 75 years: 0.2 mg of hydromorphone.

Near the end of surgery, 4 mg ondansetron will be given intravenously per clinical routine. Upon completion of surgery, sevoflurane will be discontinued. Neuromuscular block will be reversed with sugammadex per clinician preference. At the end of the surgical procedure, patients will be extubated and transferred to the post anesthesia care unit (PACU).

Surgical pain will be treated with boluses of intravenous morphine/ hydromorphone per clinical routine by nurses blinded to intraoperative randomization. PCA will be activated upon arrival to PACU, per routine care. Generally, rescue boluses are given when verbal response pain scores are  $\geq 4/10$ , but consistent postoperative analgesic management will be at the discretion of the postoperative clinical team. Nausea and vomiting will be initially treated by intravenous injection of 4mg ondansetron per clinical routine. Alternative anti-emetics will be administered as clinically indicated.

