## Background

Opioid requirements in hospitalized patients varies at least ten-fold depending on a host of factors, many of which are unknown to clinicians or poorly characterized in medical records. Important factors include genetic sensitivity, alcohol consumption, previous opioid use, pain intensity etc. Even within specific categories, say chronic opioid users, there is tremendous variation in sensitivity — and thus opioid requirement under various conditions.

In most situations, patients can simply be queried about pain, and their responses used to guide analgesic administration. But during anesthesia, patients do not experience pain (a conscious response). But patients nonetheless clearly experience and respond to nociception even during general anesthesia. Increases in blood pressure and heart rate roughly indicate when patients are experiencing nociceptive stress, but neither is reliable. No other routine anesthetic monitors provide useful indications of nociceptive intensity.

Even experienced anesthesiologists cannot reliably predict or estimate opioid requirements in individual patients. Consequently, most routinely give small amounts of opioid during general anesthesia, and often give a bolus of a slow-onset, long-acting opioid such as morphine or hydromorphone at the end of surgery to provide analgesia during the initial hours of post-anesthetic recovery. The doses given, while reasonable *on average*, often prove inadequate or excessive for individual patients. Those given too much awaken slowly at the end of anesthesia and may breathe poorly; those given inadequate doses suffer intense pain upon awaking and it often takes many boluses of opioid and considerable time to control their pain.

There are now several devices that estimate nociception during general anesthesia including the Surgical Pleth Index, pupillary reflexes, galvanic skin responses, and heart-rate variability. The best-validated system is the PMD-200 system from Medasense (Ramat Gan, Israel). It is comprised of a console and designated finger probe and a single-use sensor. The PMD-200 acquires 4 signals: photoplethysmography, galvanic skin response, accelerometry, and skin temperature. Based on a random forest analysis, the device generates the NOL index. The intended use of NOL is to assess nociception input during general anesthesia.

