NOL is a unitless index that extends from 0 to 100, with values exceeding 25 indicating that patients are experiencing substantial nociceptive input. Previous work in anesthetized patients has shown that NOL values are low in the absence of nociceptive input (e.g., when unstimulated) and progressively increase in response to progressively more intense stimuli (e.g., tetanic electrical stimulation, skin incision, and intubation). At

this point, there are only limited data — largely unpublished — showing that titrating intraoperative opioids to NOL improves post-anesthetic recovery.

Most studies of NOL titration and recovery characteristics were conducted with remifentanil infusions, using target-controlled infusion, an opioid-dosing technique that is rarely used in the United States and not approved by the Food and Drug Administration. Whether intraoperative titration will improve recovery characteristics will depend critically on the choice of opioid(s). Remifentanil is easy to titrate because the drug is potent and ultra-short acting. Patients given remifentanil are thus usually given a bolus of long-acting opioid such as morphine or hydromorphone near the end of surgery to bridge the analgesic gap between remifentanil discontinuation and arrival in the PACU. Thus, PACU recovery characteristics are largely determined by the long-acting opioid bolus timing and dosage which is given empirically and independent of NOL guidance.

Fentanyl is probably the ideal intraoperative anesthetic for NOL testing because of its intermediate and context-sensitive half-life (effect is proportional to not just dose but duration of administration). Fentanyl is initially short acting (typically 15 minutes) and thus easy to titrate. Its action is not terminated by metabolism; instead, the lipophilic drug redistributes into fat tissue. But after several hours of administration, much of the fat reservoir fills, and the drug's effect then becomes constrained by rate of metabolism, and can exceed the duration of morphine effect. Fentanyl is thus initially short acting, when titration is necessary, but then becomes long-acting and remains effective at least during the initial part of recovery. Patients who have long operations ( $\geq 2$  hours) who are given the “right amount” of intraoperative fentanyl have effective pain control without use of a long acting opioid.

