### ***Aim of this study:***

Demonstrate that **intraoperative NOL-guided titration of fentanyl improves initial recovery characteristics**. All times below are relative to when sevoflurane anesthesia is discontinued.

**Primary hypothesis.** Pain scores (0-10 verbal response scale) at 10-minute intervals during the initial 60 minutes of recovery are less in patient with NOL-guided fentanyl than with routine care, with 1 point being considered a clinically meaningful difference

**Primary Outcome.** Pain Scores at 10-minute intervals during the initial 60 minutes of recovery

**Secondary hypothesis.** NOL patients are more likely to have a “good” pain scores, defined as < 5 (i.e., 0,1,2,3 or 4) across the measured intervals, with a relative 10% or more increase in the proportion of good scores being considered clinical meaningful.

**Secondary Outcome.** Whether or not the pain score at any measured interval is < 5.

We will also consider several exploratory hypotheses.

**Exploratory hypothesis 1.** Fewer analgesic rescue boluses are required in NOL-titrated patients during the initial 60 minutes of recovery.

**Exploratory hypothesis 2.** NOL-guided patients are no less alert (Ramsay score) during the initial 60 minutes of recovery than those given fentanyl per routine, based on a clinically meaningful non-inferiority delta of 20%.

**Exploratory hypothesis 3.** Emergence from anesthesia (discontinuation of sevoflurane anesthesia to extubation) is faster in NOL-guided patients.

**Exploratory hypothesis 4.** Fewer NOL-guided patients experience post-operative nausea and/or vomiting (PONV) **at least once** during the initial 60 minutes of recovery.

**Exploratory hypothesis 5.** There are fewer episodes of inadequate analgesia (too much or too little) in NOL-guided patients. Inadequate analgesia will be defined by systolic pressure  $\geq 140$  mmHg, heart rate exceeding 90 beats/min, diaphoresis, tearing, or movement. Excessive anesthesia will be defined by MAP  $< 65$  mmHg or BIS  $< 40$ . All values must return to normal for at least 15 minutes for a subsequent deviation to be

considered a new episode. The outcome for a patient will be the number of episodes.

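### The Protocol section rules out long-acting opioids, then schedules a hydromorphone bolus before the end of surgery without saying which arm or arms receive it

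*Combined protocol and SAP*

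**What the plan says.** The Protocol section sets opioid rules before it introduces randomization and the two arms, so they read as applying to everyone. Three consecutive sentences matter:

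- The first limits the choice of drug and allows an exception for clinical need: "Unless another opioid is clinically indicated, fentanyl will be the only opioid used for induction and throughout anesthesia".
- The second bans a whole class and carries no exception: "Long-acting opioids such as morphine will not be given".
- The third deals with the interval before the PACU and again allows an exception: "No opioid will be given unless clinically indicated from the end of surgery until patients reach the recovery unit".

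Items 1) and 2) then describe fentanyl dosing under routine care and under NOL guidance. After item 2), in a paragraph with no heading and no arm label, comes: "Approximately 20-30 minutes before end of the surgery, a preemptive bolus of hydromorphone will be given intravenously per clinical routine". Dose bands by age and weight follow, from 0.2 to 0.6 mg. The text continues with ondansetron, reversal, extubation and PACU care.

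The Background describes usual practice as one in which anesthesiologists "often give a bolus of a slow-onset, long-acting opioid such as morphine or hydromorphone at the end of surgery". It goes on to prefer fentanyl for testing NOL, because patients having long operations who receive the right amount should have adequate pain control without a long-acting opioid.

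**The concern.** One part of the section forbids what another part of it orders. The drug concerned is an analgesic given shortly before the primary outcome, which is pain over the first 60 minutes of recovery.

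Two things are at stake. The first is what treatment is being tested. The Background argues for fentanyl because it should make a long-acting bolus unnecessary. Writing of remifentanil anesthesia, it warns that "PACU recovery characteristics are largely determined by the long-acting opioid bolus timing and dosage which is given empirically and independent of NOL guidance". A scheduled bolus of that kind brings back the feature that fentanyl was chosen to avoid.

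The second is attribution. The Measurements section says that the anesthesia clinicians cannot be blinded. Clinicians who know the arm and face two conflicting rules could resolve them differently in the two arms, particularly since the bolus is written directly below the NOL-guided item and nothing matching it appears under routine care. Any resulting difference in hydromorphone use would be mixed with the effect of NOL guidance.

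**Working it through.** The plan gives no figure that turns on this point, so there is none to reproduce. The check is a comparison of text, followed by simple arithmetic on timing and reach.

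**1. Is hydromorphone covered by the ban?** Yes, on the protocol's own terms. The Background twice names it beside morphine as an example of a long-acting opioid.

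**2. Does the bolus fall within the period the rules govern?** Yes. It is due 20-30 minutes before the end of surgery. The Protocol section says "Upon completion of surgery, sevoflurane will be discontinued", and the Measurements section defines that moment as the end of anesthesia. The bolus is therefore given during anesthesia.

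**3. Does the clinical-indication exception remove the conflict?** Not clearly. It appears in the sentence before the ban and in the sentence after it, but not in the ban. Even if it is read across, it speaks to an individual patient's need, whereas the bolus is scheduled for everyone by age and weight.

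**4. Which arm?** The evidence is as follows.

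| Points to both arms | Leaves it open |
|---|---|
| The bolus is described as clinical routine | It follows item 2), the NOL-guided arm |
| Doses depend on age and weight, not on NOL | Item 1), routine care, has no counterpart |
| The text runs on to care common to all patients | No sentence names the arm or arms |
| Human Subjects Protection calls NOL titration the only non-standard element | |
| The list of changes enters the bolus without an arm label, beside fentanyl entries that carry one | |

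Both arms is the likeliest reading, but it has to be inferred.

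**5. Timing relative to the primary outcome.** The aims state: "All times below are relative to when sevoflurane anesthesia is discontinued". The window is 60 minutes, and the Data Analysis section models 7 time points at 10-minute spacing, which implies a score at time zero. Taking sevoflurane to stop at the end of surgery:

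- Earliest score: 20 + 0 = 20 minutes after the bolus.
- Latest score: 30 + 60 = 90 minutes after the bolus.

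The Measurements section instead counts scores from awakening. On that clock both limits move later by the emergence time, which the documents do not give.

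**6. Reach.** The maximum is 144 patients randomized 1:1, so 144 are affected if the bolus is for both arms and 144/2 = 72 if for one.

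**7. Possible bias.** Let q be the difference between arms in the proportion receiving the bolus, and h its effect in pain points. The contribution to the observed difference is q × h. If q = 0, it is 0. The documents give neither q nor h. As an illustration only, with assumed products set against the 1.25-point design difference in the sample size section:

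| Assumed q × h (points) | Share of 1.25 |
|---|---|
| 0.25 | 0.25/1.25 = 20% |
| 0.50 | 0.50/1.25 = 40% |
| 0.75 | 0.75/1.25 = 60% |

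No estimate of dilution is offered for a bolus given to both arms. The list of changes records the bolus and the rewritten statistical section together, so the 1.25 points may already allow for it.

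**The case against.** The strongest reply is that this is an editing omission with a readable intent. The bolus instruction is specific about drug, route, timing and dose. The ban is general and stands between two sentences that allow for clinical need. The list of changes shows that the bolus was added on purpose, so the ban may be left over. That probably explains how the conflict arose, but both sentences remain in force and a site following the plan would still have to choose between them.

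It can also be said that the arm question is thin. Ondansetron, reversal and PACU analgesia also appear only after item 2), and nobody would take those as confined to the NOL arm. Paragraph layout may also have been lost in the extracted text. This stands, and is why both arms is accepted as the likeliest reading. What remains is that the protocol should say so.

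Third, if both arms receive the bolus alike, the randomized comparison, the type I error and the primary model are unaffected. That is correct. The percentages above rest on assumed inputs and are not evidence that bias exists.

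Fourth, the Background sentence about PACU recovery concerns remifentanil, and its claim for fentanyl is conditional on long operations and the right dose. Both limits are real. The passage shows only that the protocol recognizes such a bolus as able to drive this outcome.

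Finally, the exclusion of patients whose clinician prefers an additional opioid concerns preference, not a scheduled drug. That link is weak, so the criterion needs checking but is not itself shown to be wrong.

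**Conclusion.** The concern holds. Two current instructions in the Protocol section contradict each other on whether a long-acting opioid is given during anesthesia, and the arm or arms meant to receive it are not stated. This is a contradiction between stated treatment rules, not a missing detail.

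The scheduled amount is 0.2-0.6 mg under one instruction and none under the other, for up to 144 patients, about 20 to 90 minutes before the primary pain scores. The interval assumes that sevoflurane stops at the end of surgery and that scores are timed from that point.

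The effect on the treatment comparison is zero if both arms receive the bolus alike, and of unknown size if they do not. Even in the first case, the ban and the Background rationale misdescribe the regimen under test. Because the conflict sits immediately ahead of the primary outcome and the intraoperative clinicians know the allocation, it must be fixed.

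**What to change.** 1. Reconcile the opioid rules at the start of the Protocol section with the hydromorphone paragraph, so that only one instruction remains. Which rule is right is a clinical decision for the investigators, and none is proposed here.
2. Put the reconciled instruction in text that states expressly which arm or arms it covers.
3. Align the Background rationale with it, and check exclusion criterion 2 against the result.
4. Add a descriptive table of hydromorphone receipt, dose and timing by arm.
5. If the arms are meant to differ, state the conclusion as a comparison of treatment packages, not of NOL-guided fentanyl alone.

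The cost is a wording amendment and one table, with no extra patients or procedures. The Measurements section already has anesthetic drugs recorded electronically. It does not name hydromorphone, and the list of medications entered on the PMD-200 monitor does not include it, so the team should confirm that the electronic record captures its dose and time.
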